11.0 Research Methods & Procedures

Provide a detailed description of the methods and procedures that will be used to carry out the study. Include a summary of study visits and procedures (i.e., schedule of events table) in the space below or as an attachment.

Please make sure to include:

- Dosing of drugs and other details of study drug administration and study treatments
- A list and description of any experimental procedures
- A list and description all tests & procedures that would not be done if the subjects were not in the study
- An explanation how study participation differs from the standard of care
- Procedures being performed to monitor subjects for safety or to minimize risks

Interventions: 4 weeks

- Treatment will start (week 1) with 4 consecutive rTMS and 2 PT sessions (skipping weekends)
- Sessions will continue at 2 times a week for a total of 10 sessions
- Measurements will occur at:
 - The first visit (except GROC)
 - The last visit of each week
 - At 4 time points after the termination of the interventions-via e-mail survey
 - 4 weeks
 - 3 months
 - 6 months
 - 1 year

First Session:

- Screening (Budapest Criterion, and TMS screening)
- Informed consent- during the phone screening subjects will be given the opportunity to have informed consent documents sent to them via email. Subjects will be given time to read the documents and ask questions about the study before agreeing to participate.
- Randomization
- Baseline measurements
- rTMS/sham rTMS session
- PT session

Subsequent Sessions (9):

- TMS screening
- rTMS/sham rTMS (the first week 2/4 sessions will not include a PT session)
- PT session
- Repeat measurements will be taken at the end of each week (4 in total)

Test and measures: All outcome measures are self-reported and collected using REDCap.

- Primary
 - Numeric Pain Rating Scale (NPRS) (0-10): Average score for the week

- Secondary Measures

- Numeric Pain Rating Score (0-10): Worse and least pain intensity over past 24 hours
- NIH Patient-Reported Outcomes Measurement Information System (PROMIS): Pain interference, pain behavior, physical functioning, satisfaction with discretionary social activity, satisfaction with social roles, fatigue, depression, anxiety, and anger.
- Patient Global Impression of Change (GROC) (only measured at follow-up)- scale rated from 0 (not important) to 7 (a very great deal important).

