- Patient Global Impression of Change Impact (GROCI) (only measured at follow-up)- scale rated from 0 (not important) to 7 (a very great deal important).
- Patient Acceptable Symptom State (PASS): “Considering all the different ways your pain symptoms are affecting you, if you were to stay in this state for the next few months, do you consider that your current state is satisfactory?” (Yes/No)
- Grip Strength (Subjects with UE symptoms only)- Measured using a dynamometer bilaterally.
- Leg Press 1 Repetition Maximum Test (Subjects with LE symptoms only): The subject will perform 2 warm-up sets with light resistance. Weight will be increased with the goal of finding the 1 repetition maximum weight within 4 trials. A 2-minute rest period will be given between trials.
- Patient Specific Functional Scale: Goals are set by PT and subject. The patient rates their ability to complete the task described in to goal on a 0(unable to perform) to 10 (Able to perform activity at the same level as before injury or problem).
- Adverse events
- Participant disposition: Who was enrolled/reasons for exclusion, reason for dropout (if known)

Interventions:

- rTMS:

- rTMS will be delivered using a commercially available magnetic stimulator (Rapid², Magstim Inc., Eden Prairie, MN) with a figure-of-8 coil at 10 Hz. With subjects in a seated position, the coil will be positioned on the scalp, contralateral to the subject’s symptomatic side. Coil orientation will be optimized for stimulation of the abductor pollicis brevis.
- Targeting:

Subjects will wear a lycra cap so marks can be made to facilitate proper targeting. Single-pulse stimulations will be delivered over various locations of the contralateral primary motor cortex to identify the optimal location for stimulation of the target muscle. Motor evoked potentials (MEP) of the abductor pollicis brevis will be monitored using electromyography (EMG) (Motion Lab Systems Inc., Baton Rouge, LA). Once the optimal stimulation position is identified a mark will be made on the lycra cap. The motor threshold (MT) of the muscle will then be

identified by systematically adjusting the pulse intensity. The MT will be considered the lowest stimulation intensity at which 5 out of 10 MEPs have a peak-to-peak amplitude of at least 50 microvolts, measured using RMG of the abductor pollicis brevis.

○ Parameters:

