rTMS will be performed at the identified optimal location at 10Hz using an intensity that is 80% of the MT. Pulse trains will be delivered for 10 seconds, with a 30 second rest for 20 repetitions. This will result in a total of 2,000 pulses of magnetic stimulation.

○ Safety:

The most common side effects during stimulation are local discomfort and headaches. Subjects will be asked to inform the researcher if they are unable to tolerate the rTMS. If they cannot tolerate the stimulation the subjects will be given two options. The first option will be to reduce the stimulation intensity to a point that is tolerable. The second option will be to stop the stimulation. If they elect to stop the stimulation the subject can decide to end participation in the study or try another session at a subsequent date. Subjects will also be monitored for EMG activity at the abductor pollicis brevis and visual twitch response at other muscles. If this activity increases over the course of the stimulation the intensity will be reduced.

- Sham rTMS:

- Sham rTMS will be performed using the same coil and delivery device used in the real rTMS group. The sham group will start with the same localization procedure as the real rTMS group. The magnet will then be moved over the vertex of the skull and the intensity will be dropped to 5% of the maximal stimulation output or half of the treatment intensity (40% of MT) used in the real rTMS group, whichever is lower. Subjects in both groups will be told that after localization, the stimulation intensity will be lowered for the treatment. The sham group will be told that with this lower intensity they may experience minimal to no sensation from the stimulus. Allocation will be disclosed to all participants after the last data collection timepoint.

- Rehabilitation:

- Rehabilitation will consist of education, value-based goal setting, Graded Motor Imagery (GMI) (3 components described below), meditation, and graded activity. Subjects will complete activities at treatment sessions and be asked to perform certain treatment activities at home.

- Week 1: Pain education, functional value-based goal setting, laterality training (first component of GMI), one task for graded activity (task-based on patient goals)
 - Week 2: Continue week 1 activity, add graded motor imagery (second component of GMI), progress 1st graded activity, and initiate 2nd graded activity exercise.

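### Randomisation comes before the motor-threshold step that both arms share, and the plan has no rule for a subject without a threshold: loss could differ by arm, and reordering is a cheap improvement

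*Combined protocol and SAP*

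**What the plan says.** - **Order of the first session (section 11.0, First Session).** After screening and consent, the list runs "Randomization - Baseline measurements - rTMS/sham rTMS session". Localisation and threshold finding are described only within the intervention, so they follow allocation.
- **Localisation (section 11.0, Sham rTMS).** "The sham group will start with the same localization procedure as the real rTMS group".
- **Threshold (section 11.0, Targeting).** MT is the "lowest stimulation intensity at which 5 out of 10 MEPs have a peak-to-peak amplitude of at least 50 microvolts", recorded by EMG at a thumb muscle.
- **Real intensity (section 11.0, Parameters).** "rTMS will be performed at the identified optimal location at 10Hz using an intensity that is 80% of the MT". No alternative is given for a subject in whom no MT is found.
- **Sham intensity and site (section 11.0, Sham rTMS).** The coil goes to the vertex instead of the located site. On intensity, the text reads: "the intensity will be dropped to 5% of the maximal stimulation output or half of the treatment intensity (40% of MT"); the lower of the two applies.
- **Eligibility (sections 7.1 and 7.2).** A measurable MT is not among the criteria.
- **Blinding (section 4.1).** Patients and physical therapists are blinded. The researcher giving rTMS is not.
- **Primary analysis (section 18.3).** It is restricted to those who complete 80% of the treatment.

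No section says what happens, in either arm, when an MT cannot be obtained.

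**The concern.** A step that both arms receive identically, and that can fail, is placed after allocation. Its result matters more for one arm: the real intensity has no value without an MT, while the sham coil position does not use the located site and the sham rule contains a term that does not use MT. With no written rule, the decision about such a subject falls to study staff. If the unblinded researcher also does the localisation, as the plan implies, that decision is made with the arm known.

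What is at stake is selection after randomisation. If subjects without an MT left the real arm but stayed in the sham arm, the primary analysis would compare a filtered group with an unfiltered one. There is some reason to think that failure might not be random. The coil is placed opposite the symptomatic side, so in upper-limb subjects the recorded thumb muscle would be in the affected limb, and section 7.1 lists weakness, tremor and dystonia among the diagnostic features. That is an inference; the documents do not say that failure tracks severity.

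**Working it through.** **1. Does the sham rule need an MT?** The rule takes the lower of 5% of maximal output and 40% of MT. The second term is lower only if 0.40 × MT < 5%, that is, if MT < 5/0.40 = 12.5% of maximal output. If MT is too high to measure (above 100% of output), 40% of it would exceed 40% of output, so the 5% term applies. Sham can then be set without an MT value. The real rule, 80% of MT, cannot.

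**2. How many subjects might be affected?** The documents give no failure rate; 2%, 5% and 10% are assumptions. With n subjects in the real arm and failure rate p, the expected number is n × p and the chance of at least one is 1 − (1 − p)^n. The main case is n = 15, half of the 30 in section 2.1. The other columns use the 10 completers per group of section 5.2 and half of its cap of 36.

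| Assumed rate | n = 10 | n = 15 | n = 18 |
|---|---|---|---|
| 2% | 0.2; 18% | 0.3; 26% | 0.36; 30% |
| 5% | 0.5; 40% | 0.75; 54% | 0.9; 60% |
| 10% | 1.0; 65% | 1.5; 79% | 1.8; 85% |

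For example, 1 − 0.95^15 = 1 − 0.463 = 54%.

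**3. What would that do to power?** The plan's own figure first. Section 5.2 uses f = 0.274, 2 groups, m = 4 measurements, correlation ρ = 0.5, nonsphericity 1 and alpha 0.05. For the group-by-time interaction, λ = N f² m/(1 − ρ) = 20 × 0.274² × 4/0.5 = 12.01, with 3 and (20 − 2) × 3 = 54 degrees of freedom. Power is 81.1%; N = 18 gives 75.9%. The stated total of 20 is reproduced.

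For one-sided loss, λ is multiplied by 4n₁n₂/N². If real-arm completers are lost and not replaced:

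- 9 v 10: λ = 19 × 0.274² × 8 × (360/361) = 11.38; power 78.5%
- 8 v 10: λ = 18 × 0.274² × 8 × (320/324) = 10.68; power 75.4%

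Section 2.1 continues recruitment until 20 have completed or 30 are enrolled, so lost completers may be replaced. Replacement restores numbers but does not undo selection.

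**4. What would it do to the estimate?** Dropping a share p of the real arm, whose mean outcome differs by d from those kept, shifts the real-arm mean by p × d. With p = 10% and d = 1 NPRS point, the shift is 0.1 point; with p = 10% and d = 2 points, it is 0.2 point. Both d values are assumptions. Section 5.2 plans on a 2-point change.

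**The case against.** A reader might infer that a subject without an MT cannot be treated in the real arm, will still receive sham, and so produces a one-sided loss. The documents do not go that far. They are silent on a failed threshold in both arms. The sham rule also names MT, and staff could stop such a subject whichever arm was allocated. Step 1 shows that sham could be set, not that it would be given.

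A reader might also count intolerance of the single localisation pulses as a one-sided cause. It is not: both arms receive the same pulses, so exposure to that discomfort is shared. Only a missing MT could separate the arms, and the assumed rates should be read as rates of that alone.

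Nor is it established that such a subject would complete no treatment and drop out of the primary analysis. Rehabilitation is part of the treatment, and nothing says that it stops. Section 18.3 does not define whether 80% of treatment counts rTMS, therapy sessions or visits. The removal rules count missed attendance, and they disagree (more than 2 sessions in section 12.2, more than 3 in section 18.1), so those sections must be reconciled. A subject who attends without an MT does not plainly meet either.

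It is also fair to say that the completers-only analysis is the larger matter, and that the same unblinded researcher gives all 10 sessions. Reordering protects only the first threshold; the plan does not say whether MT is measured again later.

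All of this stands, and it limits the point to a possibility of modest size. It does not remove the gap: the sequence is stated, the handling rule is absent, and the two intensity rules depend differently on MT.

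**Conclusion.** A cheap improvement rather than a demonstrated flaw. The first session randomises before a step that is identical in both arms and can fail, only the real intensity depends wholly on its result, and no rule covers failure. Loss after randomisation could therefore differ by arm.

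The size rests on assumed failure rates. At 2% to 10% with 15 real-arm subjects, 0.3 to 1.5 subjects are expected and the chance of at least one is 26% to 79%. Losing one or two completers without replacement costs about 3 to 6 points of power, and the shift in the real-arm mean is 0.1 to 0.2 NPRS point at the 10% rate. The effect on the result is probably small. The case for acting is that the change costs almost nothing and takes away a decision that might depend on the arm.

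**What to change.** Reorder the first session: screening and consent, baseline measures, localisation and MT, REDCap randomisation, then rTMS or sham. Count subjects in whom no MT can be obtained as not randomised and report their number. State whether they count towards the enrolment cap, which is given as 30 (section 2.1), 33 (section 6.1) and 36 (section 5.2) and must be reconciled in any case. Baseline measures would then also precede allocation.

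If the present order is kept, the plan should state one handling rule that applies to both arms and report failures by arm. The clinical content of that rule is for the study team.

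**Cost.** No added procedure, visit or staff: the same steps occur in the same visit. It does need a protocol amendment with IRB approval, and it may mean a few fewer randomised subjects where section 6.3 already expects recruitment to be hard. At the assumed 2%, 5% and 10%, 30 × p = 0.6, 1.5 or 3 of 30 subjects would not be randomised; to randomise 30, 30/(1 − p) = 30.6, 31.6 or 33.3 would have to reach localisation.

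This does not cure the completers-only primary analysis in section 18.3, which is a separate issue.

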4.0 Study Design

4.1 Describe and explain the study design (e.g. case-control, cross-sectional, experimental, interventional, longitudinal, and observational). Indicate if there is randomization, blinding, control group, etc. If randomizing, explain how this will be achieved. For studies that have a complex study design (i.e., multiple arms and treatments), include a schematic diagram.

This study will have a pilot phase and a randomized phase. The pilot phase will include 1-3 subjects who will receive real rTMS and rehabilitation. Subjects in the placebo controlled randomize phase will receive rehabilitation combined with either real or sham rTMS. Randomization will be performed in REDCap and be stratified by upper or lower extremity. Randomization will occur in blocks of 4 to ensure equal distribution. Patients and the physical therapists delivering rehabilitation will be blinded to group allocation (real/sham rTMS). The researcher administering the rTMS will not be blinded.

Changes included in protocol version 2:

- Addition of new advertisement document that will be handed out by clinicians to potential subjects.
- Addition of a pilot phase that will include 1-3 unrandomized subjects.
- Adjusted the subject numbers to reflect the pilot phase subjects.
- Added [name] to the study team.
- Created new informed consent document for the pilot phase.

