Several factors that have the potential to increase the risk of seizures with rTMS have been identified. Due to the very low incidents of seizures, it is difficult to confidently know if and how much these factors increase the risk of seizure. Authors have also erred on the side of overestimation by setting a low bar for associating TMS with the seizure.^{2,5} It is likely that several of the reported seizures were convulsive syncopal episodes or seizures that were unrelated to the TMS. One of the most accepted risk factors for TMS induced seizure is a history of epilepsy.² In the Lerner study, 29% (7/24) of the seizure cases were in patients with a history of epilepsy. Cases of seizure also occurred in individuals with a history of stroke (5), psychiatric disorders treated with medications that lower the seizure threshold (3), tumors (2), and arteriovenous malformation (1).⁵ Four seizures (17%) occurred in individuals without any identifiable risk factors.⁵ Although seizure is a serious risk factor, there have been no reports of long-term deleterious effects in those individuals who had a seizure that was attributed to rTMS.

Based on this information we agree with Rossi et al that treatment with a Transcranial Magnetic Stimulator is low risk.¹ To further reduce the risk of adverse events we will follow the accepted stimulation and monitoring guidelines.^{2,6} Stimulation parameters will be at intensities below motor evoked potential, we will provide adequate time between stimulation trains, and we will monitor for increasing EMG activity in contralateral muscles.⁶ We will exclude subjects who are epileptic and who have implanted metal or electronic devices in or near their head, such as aneurism clips, stents, pacemakers, cochlear implants, implanted brain stimulators, and ocular implants. The research team will have an emergency plan in place to deal with any adverse events. Subjects receiving rTMS will be placed in a safe position that will reduce the risk of

injury if a seizure occurs. If a serious adverse event, such as a seizure occurs, the research team will call EMS services and encourage the subject to seek immediate emergency care. Subjects will be made aware of the potential adverse events during the informed consent process.

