24.0 Informed Consent

24.1 Will you be obtaining consent from subjects?

Yes *(If yes, Provide responses to each question in this Section, and upload your consent documents)*

No *(If no, Skip to next section)*

24.2 Describe how the capacity to consent will be assessed for all subjects. (See SOPs, section 14.7.2 for guidance)

The capacity to consent will be assessed during the screening process for all subjects. Subjects will be asked if they have any questions or difficulty understanding the verbal and written communication, and the associated risks of the procedures. If comprehension difficulties are present, further verbal communication will be offered (including reading the consent documents to the subject) by an investigator. Individuals who are not fluent in English will be excluded from the study.

24.3 Describe the consent process that will be conducted to ensure that subject is fully informed regarding study details and subject rights. Include where the consent process will take place, with consideration of the need to protect the subject's right to privacy.

Step 1: During the phone screening process subjects will be asked if they would like a copy of the consent documents e-mailed to them before the first visit. This will be encouraged so subjects have ample time to review the documents. Study procedures will be verbally explained to subjects using a standardized script. Subjects will be encouraged to ask questions about the study. Subjects in the pilot phase will receive a consent document that does not include information about randomization and sham rTMS. The consent document provided to subjects in

the randomized phase of the trial will contain language on the randomization process, sham rTMS, and blinding.

Step 2: During in-person screening study procedures will be verbally explained to subjects using a standardized script. Subjects will be encouraged to ask questions about the study.

Step 3: During the in-person screening potential subjects will be given 2 paper copies of the consent documents. They will be given as much time as needed to review the documents and ask questions. Subjects who agree to participate will keep one copy of the consent documents and provide a signed copy to the investigator.

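### The statement about feeling little or nothing is scripted for the sham arm only; both arms should hear one neutral statement in identical words

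*Combined protocol and SAP*

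**What the plan says.** Section 4.1 sets out the blinding: "Patients and the physical therapists delivering rehabilitation will be blinded to group allocation (real/sham rTMS"). It continues: "The researcher administering the rTMS will not be blinded".

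The Sham rTMS part of section 11.0 contains two adjacent sentences about what subjects hear. The first is for everyone: "Subjects in both groups will be told that after localization, the stimulation intensity will be lowered for the treatment". The second names one arm: "The sham group will be told that with this lower intensity they may experience minimal to no sensation from the stimulus". The real-rTMS part of the same section covers targeting, parameters and safety. It asks subjects to report stimulation they cannot tolerate, but tells them nothing comparable about how little they might feel.

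On what subjects know beforehand, section 24.3 says that the consent document for "the randomized phase of the trial will contain language on the randomization process, sham rTMS, and blinding". The same section describes the spoken explanation: "During in-person screening study procedures will be verbally explained to subjects using a standardized script". Section 19.1 adds: "Subjects will be made aware of the potential adverse events during the informed consent process".

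On outcomes, section 11.0 makes the weekly average NPRS primary and states: "All outcome measures are self-reported and collected using REDCap". Its list of first-session steps puts randomization ahead of baseline measurements.

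**The concern.** A sham control is meant to make the arms alike in everything except the active stimulation, including what subjects are told. Here the written plan has the arms receive different information. Subjects know that a sham is possible and score their own pain, so what they expect, or which arm they believe they are in, can enter the primary outcome directly.

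The trial's only hypothesis compares real with sham rTMS, each combined with rehabilitation. If the arms differ in wording as well as in stimulation, an observed NPRS difference, or the absence of one, could partly reflect the wording. No later analysis could separate the two, because wording and arm coincide completely.

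**Working it through.** No arithmetic applies. The plan states no figure on this point, and the change alters neither sample size, alpha nor power. The check is a comparison of the texts.

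1. **Is the message really specific to one arm?** The two sentences are adjacent and name different audiences: both groups, then the sham group. The authors wrote both groups where they meant both. The natural reading is that the second sentence is for sham subjects only.

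2. **Does the real arm get a matching message elsewhere?** The real-rTMS text in section 11.0, the consent process in section 24.3 and the risk text in sections 19.1 and 19.3 contain none.

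3. **When is it given?** A message that depends on the arm can be given only once the arm is known, so after randomization. The standardized script in section 24.3 belongs to the phone and in-person screening, which precede randomization. It cannot equalize something said later. The script itself is not in the documents, so some information about sensation may reach both arms through it, and some through the adverse-event disclosure. Neither cancels a later sentence given to one arm.

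4. **Who gives it?** The plan does not say. The operator, who knows the allocation, is the likely person, but that is an inference.

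5. **Can it reach the primary outcome?** NPRS is the patient's own rating, so there is a direct route. How strongly the wording acts, and which way, cannot be derived from the documents. The sentence might lower a sham subject's expectation of benefit, or it might reassure that subject that weak sensation is normal. These would push in opposite directions.

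6. **Would copying the sham sentence to the real arm solve it?** Not cleanly. Section 11.0 names local discomfort and headaches as the commonest side effects during stimulation, and section 17.1 expects scalp discomfort and muscle twitching in some subjects. A real-arm subject told only to expect little or nothing, who then feels something distinct, has gained a cue. The common wording must therefore cover the whole range of sensation.

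7. **Order at the first session.** The list runs screening, consent, randomization, baseline measurements, rTMS, physical therapy. It reads as a sequence, and on that reading allocation exists when baseline values are taken. Although section 11.0 calls every outcome self-reported, it also lists grip strength and a leg-press maximum, which are performance tests that staff would normally supervise. Section 13.1 places initial data collection and rTMS in the same laboratory and does not say who takes the baseline tests.

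**The case against.** The strongest reply is that the sentence protects the blind. It gives a sham subject an innocent reason for feeling little, and in a parallel-group trial nobody hears the other arm's script. Both points are fair, and they soften the concern. They do not justify wording for one arm only: the explanation serves its purpose equally well when both arms hear it, and expectations can differ between arms without any subject comparing scripts.

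A second reply is that the text may only be loosely drafted. The sentence sits under the sham heading, and nothing says that the real arm is denied it. That is possible. If both arms already hear it, the section is misworded and still needs editing.

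A third reply is that the harm is conjectural. This stands as far as size and direction go, and it limits how strongly the point can be put.

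On the order of steps, it can be said that baseline still comes before the first stimulation, that patients are blinded, and that nobody who knows the allocation is shown to handle baseline data. This also stands, which is why that part is minor.

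**Conclusion.** Followed as written, the plan gives the two arms different information after allocation in a trial that relies on patient blinding and a self-reported primary outcome. This should be corrected. Confidence is high on what the text says and low on how much it matters: no size or direction can be given.

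The conclusion rests on reading the second sentence as literally addressed to sham subjects, and on there being no equivalent statement in session scripts that the documents do not include.

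A reader might infer that the sentence unblinds the sham arm, or that it biases the trial in favour of rTMS. The documents support neither. The sentence does not disclose allocation, it offers a benign explanation for weak sensation, and nothing in the plan fixes which way expectation would move. Nor do the documents show that real-arm subjects are told anything contrary.

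The order of randomization and baseline is a separate, small matter of good practice. It is not evidence that baseline values would be compromised.

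**What to change.** In the Sham rTMS part of section 11.0, replace the sentence for the sham group with one statement read word for word to subjects in both arms, and cross-refer to it in the real-rTMS text. For example: after localization the intensity is lowered; sensation varies between people; you may feel some, little or no sensation. Leave the adverse-event disclosure at consent unchanged.

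In the first-session list, place baseline measurements before randomization, so that NPRS, grip strength and leg press are all recorded before any allocation exists.

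The cost is a wording edit and a reordered checklist, submitted to the IRB as section 2.1 requires for changes. No extra subjects, visits or measurements are needed. If anyone has already been randomized under the present wording, the date of the change should be recorded.

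The edit removes only the verbal difference. Sham is still delivered over the vertex at reduced output, so the two procedures may continue to feel different.
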